DARAJA Clinical Trial

Statistical Analysis Plan
Version 1.0
12 May 2023

**Reducing post-hospital mortality in HIV-infected adults in Tanzania
(DARAJA)**

Sponsored by:
National Institutes of Health

Funding Mechanism
R01

Grant Number:
MH118107-01

Trial protocol:
version 2.2, July 8, 2019

Trial registration:
<https://clinicaltrials.gov/ct2/show/NCT03858998>

Protocol paper:

INTRODUCTION

This statistical analysis plan (SAP) describes the statistical procedures that address the study objectives specified in the DARAJA Study Protocol, Protocol Paper and Trial Registration (referenced above).

The SAP is applicable to the final analyses following end line survey. The end line survey was conducted about 12 months after the final enrollment.

Study design

This is a randomized controlled trial to evaluate the efficacy of a social worker intervention in 500 HIV-infected adults who have been hospitalized in Mwanza, Tanzania.

Statistical hypothesis for primary objective

The **primary hypothesis** is that the social worker intervention will significantly increase survival at 12 months compared to controls. The study is powered to have 98% power to detect a difference in survival from 75% in the control group to 90% in the intervention group.

Analysis sets

The full analysis set is all participants in the end line survey (500 HIV adults).

Statistical analysis

Descriptive analysis

Summary statistics that are appropriate to specific variable types will be used to describe socio-demographic information of the participants in the full analysis set according to trial arm (see **shell Table 1**). Socio-demographic information were collected at baseline interview. For the descriptive analysis of the baseline characteristics, the decision to report mean (SD) or median (ranges) and the categorization of continuous variables will depend on the final distribution of these variables. These categories may be modified prior to final report to allow for optimal characterization of the respective variables. Separately, frequency, and percentages will be used to summarize participants' characteristics that were collected using categorical variables. The levels of categorical variables with few observations will be merged provided that this does not meaningfully impact on the intent of the analysis.

NB: the terms enrollment date and randomization date are used interchangeably in this document since these dates are the same for all participants.

Study endpoints

Primary endpoint: Survival at 12 months

The number of participants who die in the first 12 months post-hospitalization were recorded. Death was determined by phone calls to relatives and was confirmed by verbal autopsies, hospital records, or death certificates. Survival at 12 month was confirmed during the 12-month face to face questionnaire interview or by phone call at 12 months. We will compare 12-month survival between the intervention and control arms using the log-rank test following the intention-to-treat principle. Survival times are measured in days from the date of randomization. This is an individual randomized trial, and we anticipate the two arms will have similar baseline characteristics. Therefore, the primary analysis will be done without adjusting for baseline variables. Since we have one primary outcome, we will test the primary hypothesis without multiple testing adjustments. Statistical tests will be two-tailed, with a significance level of 0.05. If some variables at baseline are notably imbalanced, we will conduct adjusted analyses as secondary or sensitivity analysis using multivariable-adjusted Cox regression and Cochran–Mantel–Haenszel statistics. The results will be summarized in terms of survival rates as well as hazards ratios, along with confidence interval and statistical significance.

We will also conduct a secondary “per-protocol” analysis. In this analysis, we will exclude all participants who died before 90 days since these participants could not have completed all 5 sessions according to the protocol. Among participant who survived to 90 days in both arms, we will use proportional hazard cox regression to determine whether intervention participants who completing all 5 sessions experienced a lower hazards of mortality from 90 days to 1 year compared to control participants.

Secondary endpoints

The secondary endpoints considered in this analysis will be **linkage and other steps in the HIV Care Continuum**. Most secondary outcome variables will be determined by medical record extraction from the HIV clinic electronic medical record (except ART adherence). Medical record extraction was performed every 3 months using a standardized CRF ("Follow-up Medical Records Data Extraction Form").

Linkage and ART initiation will be defined as the first visit to the outpatient HIV clinic after enrollment and the time of ART initiation, respectively. Twelve-month retention will be defined as being alive and on ART between 10 and 12 months. HIV RNA levels are retrieved from the EMR. HIV viral suppression will be defined as being alive and on ART with a plasma HIV RNA level <1,000 copies/ μ l according to the World Health Organization definition. Participants who have \geq 1,000 copies/ μ l will be considered unsuppressed. Adherence will be measured with a 4-day recall questionnaire during the 12 month interview.

Time to linkage and ART initiation will be measured in days from the date of randomization to the first HIV clinic (CTC) visit or ART initiation, respectively. For participants without linkage, follow up time will be censored at the date of lost-to-follow up (defined as the date that the research team last had contact with the participant by phone call or face-to-face visit), death, or study end, whichever happens first. Time to linkage and ART initiation will be compared between groups using the log-rank test. We will conduct adjusted analyses using Cox regression. HIV clinic retention, ART adherence and viral suppression will be treated as binary outcomes at 12 months. We will compare these outcomes between study arms using the Fisher exact test. We will conduct adjusted analyses using multivariable adjusted logistic regression. Cochran–Mantel–Haenszel statistics will be used for subgroup analyses.

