The **250** participants randomized to the DARAJA intervention group will meet with a social worker in the hospital on the morning of discharge as described previously (**see C.1 Pilot Study of DARAJA Social Worker Intervention**). The second visit will be in the home, and then there will be three subsequent visits either in the patient's home or in the outpatient HIV clinic during the ensuing 3 months (total of 5 social worker visits). Of note, the social worker will be blinded to those participants enrolled in the control group.

Research Schedule, Measures, and Outcomes: A research schedule with the timing of study visits, measures, and outcomes for all 500 participants is provided in **Table 3** on the next page. These are in addition to the routine care or DARAJA social worker visits. All 500 participants in both study groups (control and DARAJA) will have three face-to-face visits and six phone interviews with a research assistant over 24 months. The **enrollment, 12 month, and 24-month** visits will be **face-to-face**. At 3-month interval phone calls, the research assistant will interview the participant about health status, clinical visits, and psycho social factors. The data managers will also extract information on clinic attendance, medications, and laboratory studies from the HIV Clinic EMR every three months. We will continue follow-up for 24 months to measure sustainability of the intervention. A description of the primary and secondary outcomes for each of the study aims is provided below:

Survival: Deaths will be documented by four methods. **1)** If a study participant misses a visit or does not respond to a phone call, then the research assistant will telephone the contacts and inquire about the participant's status. **2)** If neither the study participant nor the designated contact persons are available, a home visit will be made by a field worker. **3)** If the family reports that the participant was hospitalized, we will review hospital records. **4)** Tanzania has a well-organized system for death certificates, and nearly 100% of people who die in Mwanza have a death certificate. We will obtain copies of death certificates for all participants who cannot be contacted or who are reported deceased by a family member. The final cause of death will be decided by an adjudication committee consisting of the PI, [name] and [name].

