5) **ART adherence** will be assessed using the ACTG 4-Day ART Recall Questionnaire based on the 12 month research visit or phone call. Poor adherence will be defined as missing one or more pills in the past 4 days. Participant who died or withdrew before 12 months will be excluded from the analysis. Stratification will be used to adjust for competing risks, if necessary.

Intervention fidelity and completion

An experienced social scientist independent of the conduct unannounced field visit to observe approximately 5% of the intervention sessions of each social worker. The social scientist observed and rated the fidelity of the intervention session using a structured form including the four core elements of DARAJA intervention. A score was provided on a scale of zero to four for each observed intervention session. We will report the average fidelity scores. We will also report the number of intervention participants who completed all 5 prescribed sessions and reasons for participants who did not complete all 5 sessions including died vs. unavailable vs. moved before completing all 5 sessions.

Subgroup analyses

[figure not shown]
For any primary or secondary outcomes that are statistically significant, we will conduct subgroup analyses to see if the effect differs by sex. For time-to-event analyses, stratification and interaction p-values will be used to assess for effect modification. For categorical outcomes, stratification with Cochran–Mantel–Haenszel statistics will be used determine if the benefit/harm of the intervention differed significantly by age group (<> median age), sex or any other variables of particular interest.

Proposed tables and figures

Proposed Table 1: Baseline characteristics among participants in DARAJA clinical trial (with question numbers from the baseline survey)

Variable		Intervention (N = 250)	Control (N = 250)
		n(%)	n(%)
	Age in years (Q105 or Q106)		
sex	Sex (Q104)		
marst	Marital Status (Q108)		
head	Head of household?		
edlev	Education level (Q113)		
Insorc_recat	Occupation		
earn	Income level		
alcohol	Alcohol use (current / ever)		
antiretroviralsp	ART use (new diagnosis)		
healthinsu	Health Insurance		
	Yes		
	No		
bmi	BMI		
sbp	SBP		
cdcount	CD4		
haemoglobin	Hemoglobin		
admin_hosp	Admission Hospital		
depression	Depression (PHQ 9 < 10 vs. >=10)		
covid	COVID time period (pre COVID vs. COVID time period)		

Proposed Figure 1: Flow diagram for screening to enrollment from 20 study sites

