Proposed Figure 2: Kaplan-Meier curves for survival by study arms with log rank test (primary outcome)

Proposed Figures 3A/3B: Nelson-Aalen curves for time to linkage and ART initiation in study arms with log rank test (secondary outcomes)

Proposed Table 2: Secondary outcome table for viral suppression, HIV clinic retention, and ART adherence

Secondary Outcome	Intervention (N = ??*)	Control (N = ??*)	p-value (Fisher's exact test)
	n(%)	n(%)	
Viral load suppression (“hvl_status”)			
Suppressed			
Not suppressed			
HIV clinic retention at 12 months (“retention”)			
Retained on ART			
Not retained on ART			
ART Adherence at 12 months (“adherence”)			
100% Adherent			
Not adherent			

* N= 250 minus participants who died / withdrew

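### The secondary 'per-protocol' Cox analysis compares five-session completers with all controls alive at day 90, without adjustment; if completers are the lower-risk patients, an ineffective programme tends to show a hazard ratio below 1

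*SAP*

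**What the plan says.** The primary analysis in the SAP (Primary endpoint: Survival at 12 months) compares the randomised arms "using the log-rank test following the intention-to-treat principle". The next paragraph adds a secondary analysis that the SAP itself puts in quotation marks as 'per-protocol'. Deaths before day 90 are excluded, "since these participants could not have completed all 5 sessions according to the protocol". Then, "Among participant who survived to 90 days in both arms", a Cox model is to test if "intervention participants who completing all 5 sessions experienced a lower hazards of mortality from 90 days to 1 year compared to control participants".

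That paragraph names no covariates or weights. The only adjustment rule nearby belongs to the randomised comparison and is conditional: "If some variables at baseline are notably imbalanced, we will conduct adjusted analyses as secondary or sensitivity analysis using multivariable-adjusted Cox regression".

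Under Intervention fidelity and completion the SAP says: "We will also report the number of intervention participants who completed all 5 prescribed sessions". It will also give reasons for non-completion (died, unavailable, moved). None of this enters the Cox model. The proposed tables and figures include no output for this analysis.

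**The concern.** A control enters the comparison by being alive at day 90. An intervention participant must also have completed five sessions. This second filter acts after randomisation and in one arm only. Intervention non-completers alive at day 90 are absent from the completer group, while their control counterparts remain in the reference group. Randomisation therefore no longer protects the contrast.

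The direction depends on who completes. If frailer or less reachable patients miss sessions, completers look better than controls under a null programme. If needier patients get more contact, the bias runs the other way. The day-90 landmark is not the source of the problem: it applies to both arms and creates no false benefit under the null.

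At stake is interpretation. If the primary result were null or borderline, a favourable completer HR could be taken to show that full delivery saves lives, when part or all of it may be selection.

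**Working it through.** **Design inputs.** 250 per arm, 1:1, two-sided 0.05, 12-month survival 75% vs 90%, 10% loss to follow-up (SAP, Statistical hypothesis and Primary endpoint; Protocol, Sample Size and Power). The documents give no figure for the completer analysis, so the only stated figure to reproduce is the primary power of 98%. HR = ln 0.90 / ln 0.75 = 0.366. With 225 per arm after loss, deaths = 225 × (0.25 + 0.10) = 78.75. Freedman's formula gives √78.75 × (1 − 0.366)/(1 + 0.366) − 1.96 = 2.16, or power 0.985. This agrees and confirms the inputs.

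**Null model for the completer contrast.** Assumptions, since the documents are silent:

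- a share p of each arm would not complete, with k times the completers' hazard from day 0;
- mortality is 12% to day 90 and 12% of survivors from day 90 to 365 in both arms, so 12-month mortality is 1 − 0.88² = 22.6%;
- the programme has no effect.

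Steps:

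1. Solve (1 − p)e^(−H₁) + p e^(−kH₁) = 0.88 for completers' cumulative hazard H₁ to day 90.
2. Non-completer share among day-90 survivors: q = p e^(−kH₁)/0.88.
3. Solve (1 − q)e^(−H₂) + q e^(−kH₂) = 0.88 for completers' hazard H₂ from day 90 to 365.
4. Expected HR, completers vs all surviving controls ≈ H₂ / (−ln 0.88) = H₂ / 0.1278.

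Worked case, p = 0.20, k = 3: H₁ = 0.0932; q = 0.172; H₂ = 0.0971; HR = 0.0971/0.1278 = 0.76. Living non-completers left out: 250 × 0.88 × 0.172 ≈ 38.

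**Simulation** (5,000 null trials per scenario; Monte Carlo error about 0.01 on HR and 0.3–0.5 points on percentages). Cells show HR and the two-sided significance rate.

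| Hazard in non-completers | 5% non-completers | 10% | 20% |
|---|---|---|---|
| 3-fold | 0.93 (5.7%) | 0.86 (7.8%) | 0.76 (12.6%) |
| 2-fold | 0.96 (4.6%) | 0.92 (6.0%) | 0.84 (7.5%) |
| no link | 1.00 | 1.00 | 0.99 (4.3–4.7% across the row) |
| half | 1.03 (5.1%) | 1.06 (5.2%) | 1.12 (6.4%) |

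The closed-form HRs agree with these to within 0.01. In the same trials, comparing all day-90 survivors by randomised arm gave HR 0.99–1.01 (4.1–5.2% significant). At 2- to 3-fold, the completer analysis has a median of 43–51 deaths and leaves out about 9–10, 18–20 or 38–40 living non-completers.

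**Sensitivity to mortality.** Take 25% 12-month mortality in both arms with constant hazard. Day-90 survival is 0.75^(90/365) = 0.932, and later mortality is r = 1 − 0.75/0.932 = 0.195. With completer share c among survivors, solve cm + (1 − c)(1 − (1 − m)^k) = r for completer mortality m; HR = ln(1 − m)/ln(1 − r). For c = 0.80, k = 2: m = 0.167 and HR = 0.84; for k = 3, 0.74. For c = 0.95: 0.96 and 0.92. With more late deaths, false favourable significance at c = 0.80 rises to 9.4% (k = 2) and 23% (k = 3), against a nominal 2.5% in that direction.

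**Does baseline adjustment repair it?** 2,500 null trials per case, 20% non-completers at about 3-fold hazard, unadjusted HR 0.77–0.78. Adjusting for four baseline covariates gave 1.01 if completion depended only on them, 0.85 if half on them, and 0.76 if only on an unmeasured factor.

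**The case against.** The strongest objection is that both ingredients of harm are assumed. Nothing in the documents shows 20% non-completion or a 2- to 3-fold hazard in non-completers. Some of the text points to high completion: the protocol's pilot section reports the time spent on all five sessions per patient and clinic linkage in 31 of 31; eligibility requires willingness to have a home visit, locator details and two contacts; sessions 2–5 can come to the patient; and moving away is not clearly a marker of high mortality. At 5–10% non-completion and 2-fold hazard, the false-positive rate is close to nominal. The 5.8-fold mortality difference in the protocol's background concerns clinic linkage, not session completion. All of this stands, and it limits the size of the problem.

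It is also true that the analysis is secondary, that completion counts will be reported, and that the SAP does not say whether living non-completers are dropped or kept as a third group. The last point changes nothing: the completer-versus-control contrast is the same either way.

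Finally, adjustment is only a partial remedy, and the by-arm landmark answers a different question. Both are correct and should be stated in the SAP. None of these points supplies a safeguard for the contrast as written.

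**Conclusion.** The concern holds. As written, the completer comparison can show benefit from an ineffective programme, and nothing else in the documents corrects it. The direction is conditional on completers being at lower risk than non-completers. The size is unknown: HR 0.92–0.96 at 5% non-completion and 0.74–0.84 at 20%, for a 2- to 3-fold hazard in non-completers, over the two sets of mortality assumptions. A material distortion needs roughly 20% non-completion. The existence of the mechanism is certain; its size in this trial is not. The primary intention-to-treat result does not depend on it. This is an inexpensive correction that should be made, not a threat to the main conclusion.

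**What to change.** Revise the 'per-protocol' paragraph of the SAP as follows.

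1. Add a landmark Cox comparison by randomised arm in everyone alive at day 90, whatever the session count. Describe it as a descriptive check on the effect of assignment among day-90 survivors, not as a per-protocol estimate.
2. If the completer comparison is kept, call it exploratory and non-causal. Define completion as all five sessions done by day 90, which the 3-month session window and the SAP's own reason for the day-90 exclusion already imply. Adjust or weight for at most about four pre-named variables from Proposed Table 1, for example CD4, haemoglobin, age and ART history. With the arm term that makes five parameters: 43/5 to 51/5, about 9–10 deaths per parameter. If 10% were lost before dying, 39/5 to 46/5, about 8–9.
3. Beside the result, report how many non-completers were alive at day 90 and so left out.

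The cost is SAP wording and two Cox models on data already collected. There are two limitations to state. Baseline adjustment cannot remove selection caused by deterioration after discharge. The by-arm landmark discards early deaths and can lean slightly against the programme: halving the hazard before day 90 with no later effect gave a by-arm HR of 1.01–1.03 in simulation.

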Current Standard of HIV Care in Mwanza: We have implemented procedures to improve care for hospitalized HIV-infected patients following WHO guidelines. Of note, the PI of this proposal, [name] is an attending physician on the adult medical wards of Bugando Medical Center, and he spearheaded these improvements (14,36–41). We have expedited ART initiation following WHO guidelines, implemented routine screening and prophylaxis for TB and cryptococcus, and improved discharge planning for clinic linkage. A hospital nurse provides discharge counseling, and on the day of discharge, she accompanies patients to the HIV clinic and helps to make a clinic appointment within one-week. She also calls by cell phone the night before to remind patients to keep their clinic appointment.

HIV clinic services are provided **free-of-charge** in Mwanza including physician services, nursing care, diagnostic testing, and medications. The clinic is staffed by 5 physicians, 12 nurses, 3 data entry clerks, and 2 peer educators. In the first month at the clinic, patients are seen **weekly**; thereafter visits are monthly. Monthly HIV clinic visits include monitoring for new symptoms and assessment for medication toxicity. **One-month medication refills** are provided for the first year and every 3 months thereafter if the patient is doing well. As part of routine clinic services, plasma HIV viral load testing is performed at 6 and 12 months. Patients with a plasma HIV RNA level >1,000 copies/ μ l undergo intensive counseling with development of an individualized adherence plan. Repeat testing is performed after 3 months. HIV resistance testing is not available in Mwanza.

All clinical, laboratory and pharmacy information is routinely entered by HIV clinic staff into a standardized, national **HIV Clinic** electronic medical record (**EMR**) system. Pharmacy records including number and date of all antiretroviral drugs dispensed. All clinical data including demographics, contact information, HIV diagnoses, WHO stage, tuberculosis history, and physical exam findings are entered. Laboratory results including HIV viral load tests, CD4 T cell counts, and tests for TB, hepatitis and STIs are also entered into the EMR. The EMR database has been utilized by members of our study team in numerous studies and the quality of the data is excellent (42–44) (See Facilities and Other Resources for details).

[figure not shown]

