Linkage and other steps in the HIV care continuum: Linkage will be defined as having at least one visit to the outpatient HIV clinic. Twelve-month retention will be defined as being alive and having a clinic visit between 11 and 13 months. Twenty-four-month retention will be alive with a visit between 23 and 25 months. Adherence will be measured with a 3-day recall questionnaire and by reviewing pharmacy refill records and calculating the proportion of prescribed days of ART which are actually picked up over time. HIV RNA levels are measured routinely at the Mwanza HIV clinic at 6, 12 and 24 months, and we will retrieve results from the EMR. HIV viral suppression will be defined as a plasma HIV RNA level <1,000 copies/ μ l (15). Participants who have \geq 1,000 copies/ μ l or who do not have plasma HIV RNA level measured will be considered **virologic failures**.

TABLE 3.
RESEARCH SCHEDULE, MEASURES, AND OUTCOMES

		Month of Research Visits								
		0	3	6	9	12	15	18	21	24
RESEARCH ASSISTANT COMMUNICATIONS										
Face-to-face visits		X				X			X	
Phone call			X	X	X		X	X	X	
DEMOGRAPHICS										
Age, sex, education		*	X							
Economic status (weekly income)		*	X			X			X	
MEDICAL HISTORY										
Date of HIV diagnosis		+	X							
Prior ART use		+	X							
WHO stage		+	X	X	X	X	X	X	X	
Physical measures (height, weight, blood pressure)		+	X			X			X	
Alcohol use (AUDIT) (65,67,68)		*	X			X			X	
Depression (PHQ-9) (64)		*	X			X			X	
PSYCHOSOCIAL FACTORS										
Employment (ARTAS Baseline and Follow-up Tools) (69)		*	X			X			X	
Traditional health beliefs (HIV Knowledge Questionnaire) (70,62)		*	X			X			X	
Self-efficacy (HIV – Adherence Self-Efficacy Scale) (71)		*	X			X			X	
Transportation (ARTAS Baseline and Follow-up Tools) (69)		*	X			X			X	
Stigma (AIDS-Related Stigma Scale) (72,73)		*	X			X			X	
Social support (SPS-10) (63)		*	X			X			X	
Perceived need for HIV services (ARV Medications Attitude Scale – 15) (74)		*	X			X			X	
Physical Weakness (SF-12) (75,66)		*	X			X			X	
PRIMARY OUTCOME										
Death		¢		X	X	X	X	X	X	
STEPS IN HIV CARE CONTINUUM										
Linkage to HIV clinic (date of first clinic visit)		+		X	X	X	X	X	X	
Retention (attendance at monthly clinic visit)		+		X	X	X	X	X	X	
ART adherence (3-day recall; pharmacy refills)		*+	X	X	X	X	X	X	X	
Plasma HIV-1 RNA level			X		X		X		X	
ACCEPTABILITY										
Qualitative interviews		§					X	X	X	
COST										
Number and type of health facility visits		*+	X	X	X	X	X	X	X	

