Laboratory or radiologic services utilized		*+	X	X	X	X	X	X	X	
Medications use (prescription, non-prescription, and herbal)		*+	X	X	X	X	X	X	X	
Staff time for social worker Intervention		\$	X	X	X	X	X	X	X	

* Research assistant administered questionnaire

+ Data abstract from the HIV Clinic EMR

¢ Deaths will be documented by phone calls, home visits, hospital records, and death certificates

\$ Timing of a subset of social worker visits; social workers will also log all time spent on intervention activities

§ Qualitative interviews conducted with a subset of study participants and health care workers

Factors from the Gelberg and Andersen Model: We will measure the eight factors of the Gelberg and Andersen Behavioral Model of Health Services Utilization for Vulnerable Populations at enrollment, 3 months, 12 months, and 24 months (18). The measurement tools are listed in Table 3 and have been translated into Kiswahili and used in prior studies in East Africa (61–66).

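### The SAP omits the protocol's pharmacy-refill measure of ART adherence without explanation and leaves a 4-day self-report at 12 months as the only measure

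*SAP*

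**What the plan says.** **Protocol.** Under the heading on linkage and other steps in the HIV care continuum: "Adherence will be measured with a 3-day recall questionnaire and by reviewing pharmacy refill records". The sentence goes on to define the refill measure as the share of prescribed ART days collected over time. Table 3 repeats the pair in the row "ART adherence (3-day recall; pharmacy refills". That row carries the codes for a research-assistant questionnaire and for "Data abstract from the HIV Clinic EMR". The description of the clinic record system, under Current Standard of HIV Care in Mwanza, lists "Pharmacy records including number and date of all antiretroviral drugs dispensed". Under Research Schedule, Measures, and Outcomes, data managers are to "extract information on clinic attendance, medications, and laboratory studies from the HIV Clinic EMR every three months".

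**SAP.** Under Secondary endpoints: "Adherence will be measured with a 4-day recall questionnaire during the 12 month interview". The same section sets adherence apart from the record-based outcomes: "Most secondary outcome variables will be determined by medical record extraction from the HIV clinic electronic medical record (except ART adherence". Item 5 names the ACTG 4-day recall, taken at the 12-month visit or by phone. One missed pill in that window counts as poor adherence, and participants who died or withdrew before 12 months are left out. Shell Table 2 has one adherence outcome, fully adherent or not. On the records themselves, the SAP says "Medical record extraction was performed every 3 months using a standardized CRF".

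**The concern.** The SAP names protocol version 2.2 as its basis, yet one of the two adherence measures in that version is gone without comment. The one that remains is the subjective one. Intervention participants know they had the sessions and calls, and controls know they did not. The only blinding described is that social workers are not told who the controls are. Nothing is said about blinding the research assistants who conduct the interviews. A difference in reported adherence could therefore come partly from how people answer.

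Recall also describes only a few days near month 12, and only for those still alive, in the study and reachable. A refill measure runs over the year and can include people up to death or withdrawal.

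**Working it through.** The point is a comparison of texts and depends on no stated figure.

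**1. Side by side**

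| Feature | Protocol | SAP |
|---|---|---|
| Recall | 3-day | 4-day (ACTG) |
| Refill records | Share of prescribed ART days collected | Not mentioned |
| Source | Questionnaire and clinic records | Questionnaire only |
| Analysis time | 12 and 24 months | 12 months |
| Reason for change | n/a | None given |

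The SAP covers 12-month outcomes, so the missing 24-month analysis fits its scope. The missing refill measure has no such explanation.

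**2. What recall covers.** The window is 4 of 365 days: 4/365 = 1.1% of the first year. This describes coverage and is not a measure of bias between arms.

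**3. Who is left out.** At the planned 12-month survival of 75% and 90%, deaths alone remove 250 × 0.25 = 62.5 controls and 250 × 0.10 = 25 intervention participants. That leaves about 187 and 225 before withdrawals and missed interviews.

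**4. Are refill data available?** The protocol places the number and date of drugs dispensed in the clinic records and plans 3-monthly extraction of medication data. The SAP reports 3-monthly extraction as done and takes linkage, ART initiation, retention and viral load from it. It does not say that dispensing quantities or dates were on the form. The data were therefore held in the records and planned for extraction; their capture is not shown.

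**5. Illustration of reporting bias. All bias inputs are assumptions; none is in the documents.** Let true adherence be p in both arms, and let a fraction f of non-adherent people report full adherence. Reported adherence is p + (1 − p)f, so the spurious difference is (1 − p)(f_int − f_ctl). With p = 0.6, f_ctl = 0.3 and f_int = 0.5, it is 0.4 × 0.2 = 8 points. The table holds f_ctl at 0.3. Rejection rates for Fisher's exact test (two-sided 0.05) come from 4,000 simulated trials per cell, with 187 controls and 225 intervention participants.

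| p | f_int 0.3 | 0.4 | 0.5 | 0.6 |
|---|---|---|---|---|
| 0.6 | 0 points, 4% | 4, 14% | 8, 46% | 12, 82% |
| 0.7 | 0 points, 5% | 3, 11% | 6, 32% | 9, 67% |
| 0.8 | 0 points, 4% | 2, 8% | 4, 21% | 6, 46% |

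The range starts at no bias. The table shows that a modest difference in reporting would matter if it existed, not that it exists.

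**The case against.** The case for leaving the SAP alone has substance.

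- **Record-based outcomes remain.** Suppression and retention do not rest on self-report, adherence is one of five secondary endpoints, and the primary endpoint is death. This stands and limits the consequence. They are not full substitutes: suppression uses the latest available viral load and counts missing values as unsuppressed, and retention is on-ART status at 10-12 months.
- **The pressure to over-report may be weak by month 12.** The sessions end by about three months, the interviewer is a research assistant and not the social worker, and the documents do not say whether interviewers know the arm. This also stands; the size of any bias is unknown.
- **Recall was always planned, and refills have faults.** Collecting drugs is not taking them, and it depends on clinic attendance, which the intervention targets. That is a reason to report both measures and does not explain dropping one.

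Three stronger readings are tempting but unsupported.

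- A reader might infer that bias could equal the effect the trial is sized for. The trial is sized on a 15-point survival difference. The 10-point figure in Sample Size and Power is a remark about most care-continuum outcomes, and no bias figure is given.
- A reader might infer that the refill data already sit in the trial database. The SAP does not list those fields, its proposed flow diagram refers to 20 study sites, and completeness across clinics is unknown.
- A reader might infer that the measure was dropped after data collection. The SAP is dated after the end line survey, but that does not date the decision. The SAP also relies on a protocol paper and a registration not available here, so a change announced there cannot be excluded.

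**Conclusion.** The discrepancy is real: a measure specified in the protocol is missing from the SAP, nothing in the SAP restores or explains it, and the remaining measure is self-report from participants who know their arm. The consequence is limited to the interpretation of one secondary endpoint; the primary analysis and the record-based outcomes are untouched. The size of any bias cannot be taken from the documents, and the conclusion does not depend on the illustration. It rests on two readings: that participants know whether they had the sessions, which follows from the design, and that the current SAP text is complete on adherence. Whether the measure can still be derived depends on refill fields that the SAP does not describe.

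**What to change.** Restore the protocol's measure in the SAP beside recall:

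- **Definition.** The proportion of prescribed ART days collected, counted from the first ART prescription after randomisation to 12 months, or to death or withdrawal in an analysis that keeps those participants. Counting all days from randomisation would be a different measure: the protocol allows ART to be deferred 2 to 4 weeks in some patients, and those days would appear as uncovered.
- **Details to state.** How ART started in hospital before randomisation enters the count; how transfers and missing records are handled; and how many participants per arm have no prescription and so no denominator.
- **Reporting.** Give the proportion by arm and add a row to shell Table 2. The protocol treats adherence as binary but gives no refill cut-off, so fix any cut-off before arm-level data are seen. Label recall as the subjective measure.
- **If the refill fields were not captured,** state and justify the removal as a departure from the protocol. If the change was announced elsewhere, cite it.

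The cost is SAP wording, one derived variable and one table row if the fields exist, and a short statement if they do not. The restored measure will miss refills at clinics outside the record system, shows collection and not intake, and will overlap with retention.
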